**Table 8-1 Study VX15-809-114 Smart Adherence Technology Study Arms**

Smart Adherence Technology	Activated Features	Access to LUM/IVA Compliance Status	Number (n)
Smart Pill Bottle (Study Arm A)	Real-time dosing data transfer, electronic medication reminders/missed dose alerts (audio, visuals, texts, emails, phone calls)	Site staff and physicians, CRO, Vertex	50
Smart Pill Bottle, Control (Study Arm B)	Real-time dosing data transfer to CRO/Vertex only	CRO/Vertex only	25

CRO: contract research organization

The use of active smart adherence technologies (smart pill bottles) will provide subjects with objective and real-time feedback on dosing adherence, including reminders of upcoming or missed doses. Study physicians will access dosing adherence data and review them with subjects in Study Arm A at scheduled study visits. Subjects in Study Arm B will not receive any alerts, reminders, or real-time feedback on dosing adherence. Study Arm B will provide objective data on dosing adherence without influencing subjects to take a scheduled dose of LUM/IVA.

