## **11.3 Adherence**

### **11.3.1 Smart Adherence Technology-Reported Adherence**

LUM/IVA adherence monitoring will occur throughout the Treatment Period using smart adherence technology. This technology will allow for collection of real-time LUM/IVA compliance by reporting LUM/IVA dosing times each time the smart pill bottles are opened. Only subjects in Study Arm A will review data with study physicians at the study visits listed in [Table 3-2](#).

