### **12.3.2      Background Characteristics**

#### **12.3.2.1    Subject Disposition**

The number and percentage of subjects in each disposition category (e.g., randomized, included in the FAS, included in the Safety Set, completed study/Safety Follow-up Visit, and discontinued use of smart adherence technology or study with a breakdown of the reasons for discontinuation) will be summarized overall and by study arms.

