5 STUDY ENDPOINTS

5.1 Adherence Endpoint

This study was terminated early by a business decision. The data collected at the time of termination are limited and premature due to early termination. Therefore, the planned adherence endpoints listed in Sections 2 and 7 of the protocol will not be performed. Based on the expected available data, a list of applicable adherence endpoints below will be analyzed as follows:

- Mean percentage adherence to LUM/IVA treatment over any treatment duration for all subjects.
- Mean percentage adherence to LUM/IVA treatment over 0 through 12 weeks for subjects who have at least 12 weeks of eligible smart pill bottle data.

- Proportion of subjects with $\geq 80\%$ adherence over 0 through 12 weeks for subjects who have at least 12 weeks of eligible smart pill bottle data
- Proportion of subjects with $\geq 90\%$ adherence over 0 through 12 weeks for subjects who have at least 12 weeks of eligible smart pill bottle data

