8.2 Background Characteristics

8.2.1 Subject Disposition

The number of subjects in the following categories will be summarized overall and by study arm:

- Randomized
- Safety Set
- Full Analysis Set (FAS)

The number and percentage (based on FAS) of subjects in each of the following disposition categories will be summarized overall and by study arm:

- Completed study drug
- Prematurely discontinued study drug and the reason for discontinuation
- Completed study (defined as completed the planned study treatment and Safety Follow-up Visit)
- Prematurely discontinued the study and the reason for discontinuation

A listing will be provided for subjects who discontinued treatment or who discontinued study, along with reasons for discontinuations.

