8.3.2 Analysis of Adherence Endpoints

Mean percentage adherence to LUM/IVA treatment over treatment duration for all subjects

The percentage adherence over treatment duration for each subject is defined as:

$$100 \times (\text{total number of smart bottle openings over the eligible treatment duration excluding the physician-directed interruption periods of the eligible treatment duration}) / [2 \times (\text{eligible duration of treatment} - \text{the number of physician-directed interruption days of the eligible treatment duration})]$$

Note: (1) the physician-directed interruption is defined as the reported interruptions due to reasons not being “Non-compliance”; (2) if there are more than 2 smart bottle openings at any day, they will be counted as 2 in calculation of the adherence endpoints. (3) the eligible treatment duration = eligible date of last dose – date of first dose + 1, where the eligible date of last dose is defined to be either the CRF collected date of last dose or the last activity date of smart bottle data, whichever is earlier.

Descriptive statistics will be provided by the number of subjects (n), mean, SD, SE, median, min, and max by treatment arm based on FAS. [REDACTED]

The percentage adherence will also be listed.

Mean percentage adherence to LUM/IVA treatment over 0 through 12 weeks for subjects who have at least 12 weeks of eligible smart pill bottle data

Subjects who have at least 12 weeks of eligible smart pill bottle data are defined as those who have at least 12 weeks of eligible treatment duration = eligible date of last dose – date of first dose + 1, where the eligible date of last dose is defined to be either the CRF collected date of last dose or the last activity date of smart bottle data, whichever is earlier.

The percentage adherence over 12 weeks for each eligible subject is defined as:

$$100 \times (\text{total number of smart bottle openings over the first 12 weeks excluding the physician-directed interruption periods of the first 12 weeks}) / [2 \times (12 \text{ weeks (ie, 84 days)} - \text{the number of physician-directed interruption days of the first 12 weeks})]$$

Note: (1) the physician-directed interruption is defined as the reported interruptions due to reasons not being “Non-compliance”; (2) if there are more than 2 smart bottle openings at any day, they will be counted as 2 in calculation of the adherence endpoints.

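### Entry to the SAP's three 12-week adherence summaries depends on continued smart-bottle activity, an undefined post-randomisation outcome, and the SAP no longer tabulates who stopped using the bottle

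*SAP*

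**What the plan says.** SAP 8.3.2 scores adherence as bottle openings, capped at two a day, over two per eligible day. Physician-directed interruptions are removed from both parts. The eligible period runs from first dose to an end date "defined to be either the CRF collected date of last dose or the last activity date of smart bottle data, whichever is earlier". The SAP does not say what counts as activity. Protocol 11.3.1 describes the bottle as "reporting LUM/IVA dosing times each time the smart pill bottles are opened", which suggests an opening.

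The same date decides who enters the 12-week set, namely "those who have at least 12 weeks of eligible treatment duration". SAP 5.1 carries the restriction in the endpoint names: "for subjects who have at least 12 weeks of eligible smart pill bottle data". The 12-week denominator is 2 × (84 − physician-directed interruption days).

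Note (1) in SAP 8.3.2 states that "the physician-directed interruption is defined as the reported interruptions due to reasons not being" non-compliance. Interruptions recorded as non-compliance therefore stay in the denominator.

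On disposition, Protocol 12.3.2.1 planned counts by arm of subjects who "discontinued use of smart adherence technology or study with a breakdown of the reasons for discontinuation". SAP 8.2.1 has rows such as "Prematurely discontinued study drug and the reason for discontinuation", and an equivalent for the study, but none for the technology.

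SAP 3 explains that the trial was closed early and that only descriptive summaries remain.

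**The concern.** All four surviving adherence endpoints use this end date. For the three 12-week summaries it acts as a filter: a subject who stops opening the bottle early is removed, not scored low. Selection on a post-randomisation outcome undermines a comparison of randomised arms, even a descriptive one. The arms also differ in what could influence stopping. Arm A has reminders and reviews its data with physicians, while "Subjects in Study Arm B will not receive any alerts, reminders, or real-time feedback on dosing adherence" (Protocol, text with Table 8-1). If stopping differs by arm, the contrast could be distorted in either direction.

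The report would not show how far this happened. The n and the listed percentages do not say why a subject is absent, and the disposition row that would have said so is gone.

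**Working it through.** **Plan's own figure.** SD 8, difference 5.6, n = 50 and 25, two-sided 0.05: the t-test power is 80.5% against the stated 80%. This reproduces and is not in dispute. Of these inputs only the SD is used below.

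**How the rule behaves (activity taken as an opening).**
- Entry needs (eligible last date − first dose + 1) ≥ 84. A last opening on Day 83 gives 83 days, so the subject is out. Day 84 gives 84, so the subject is in if the CRF last dose is also Day 84 or later.
- Subject X opens twice daily on Days 1–42 and never again. All-duration score: 84/(2 × 42) = 100%. X is excluded at 12 weeks; the fixed denominator would give 84/168 = 50%.
- Subject Y is identical but opens once on Day 84, with CRF last dose on Day 84 or later. Y is included at 85/168 = 50.6%.

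**When the bottle clause matters for the all-duration endpoint.** End X's period at the CRF last-dose date instead:
- CRF Day 42: 84/84 = 100%, no change.
- CRF Day 56: 84/112 = 75%.
- CRF Day 84: 84/168 = 50%.

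In the last two cases at least one dose was reported without an opening, so 75% and 50% are lower bounds on X's dosing. No opening follows the last opening, so the clause can shorten the denominator but not the numerator. It can only raise a score or leave it unchanged. A final non-compliance interruption with no later dose lies beyond both dates, so neither rule counts it.

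**Direction at 12 weeks.** Assume perfect use to day s and missed dosing after it. The fixed score is 100 × s/84:
- Day 67: 79.8%; Day 68: 81.0%; Day 75: 89.3%; Day 76: 90.5%; Day 82: 97.6%.
- Against an arm mean of 90%, exclusion raises the mean for s = 1–75 and lowers it for s = 76–83. Excluded subjects with s = 68–83 would have met ≥80%; those with s = 76–83 would have met ≥90%.
- One such subject in an arm of n, the others at 90%, shifts the mean by (90 − score)/n. For n = 10 / 25 / 50 this is +4.0 / +1.6 / +0.8 at s = 42 (score 50), and −0.8 / −0.3 / −0.15 at s = 82.

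**Illustrative size.** Assumed inputs: use u while using the bottle, stop share p, stop day uniform on Days 1–83 (mean s/84 = 0.5), and share f of stops that are missed dosing. The SAP 12-week mean is u. The true mean is u(1 − pf/2).

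| Assumption | SAP result | True result at f = 0 / 0.5 / 1 |
|---|---|---|
| One arm, u = 90, p = 20% | mean 90 | 90 / 85.5 / 81 |
| A vs B: u 90 vs 90, p 10% vs 30% | difference 0 | 9f = 0 / 4.5 / 9.0 |
| A vs B: u 90 vs 85, p 20% in both | difference 5.0 | 5 − 0.5f = 5.0 / 4.75 / 4.5 |
| A vs B: u 90 vs 85, p 30% vs 10% | difference 5.0 | 5 − 9.25f = 5.0 / 0.4 / −4.25 |

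In the last row the sign changes only if f exceeds 5/9.25 = 0.54.

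**Proportion at ≥80%** (simulation of 400,000 subjects, u = 90, p = 20%, f = 1):
- Every subject at the same 90% dose probability: 1.00 under the SAP against 0.82.
- Between-subject SD of 8 points (beta distribution): about 0.88 against 0.72.

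The first pair assumes no between-subject spread, so the second is the more realistic.

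**Internal consistency.** SAP 8.3 includes measurements after treatment discontinuation and applies the Appendix B visit windows. SAP 8.1 exempts bottle-reported adherence from those windows. SAP 8.3.2 stops the count at the earlier date. The three do not fit together.

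**The case against.** The strongest reply is that the rule guards against scoring lost data as missed doses. SAP 8.1 foresees bottle malfunction. Protocol 10.1.2 splits each three-month supply over four bottles with one activated at a time, so drug could be taken from a bottle that is not recording. A silent bottle is therefore not proof of a missed dose. This stands, and it is why the current version should be kept.

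Second, the endpoint names disclose the restriction, and counting self-stopped time as missed measures persistence as well as use, which is a different quantity. That is fair, but disclosure does not remove the dependence on a post-randomisation outcome.

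Third, other outputs help. Exposure by arm (SAP 8.2.5) uses dose dates, so comparing the numbers with more than 12 weeks of exposure with the 12-week n roughly shows who is absent for bottle reasons. Tablet-count compliance (SAP 8.2.6) runs over days in the study. These are partial cross-checks: neither identifies a subject who stayed on drug but stopped using the bottle, nor gives the reason.

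Fourth, the analyses are descriptive, and text is redacted after both mean-adherence summary sentences in SAP 8.3.2. No claim is made that a sensitivity analysis is absent from the redacted text.

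**Conclusion.** The point holds for the 12-week summaries. On the reading that activity means an opening, entry depends on continued bottle use, and the SAP drops the disposition row that would show it. Where the silence is missed dosing, the 12-week results are expected to be too high, though stops close to Day 84 can act the other way. Where it is device failure, use of a non-activated bottle or administrative truncation, this bias does not arise. All magnitudes above rest on assumed stop rates, stop times and f; the documents give none of these.

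The documents do not support three stronger readings that a reader might infer:
- *A final silent run is never counted as missed.* This depends on the undefined word. If activity includes other device signals, a bottle that transmits but is not opened would still accrue missed doses.
- *The all-duration endpoint is inflated for anyone who gives up treatment.* If the silence is wholly missed dosing and the CRF date is accurate, the CRF last dose coincides with the last opening and the bottle clause changes nothing.
- *The reported contrast favours Arm A.* Stopping could differ by arm, but its direction and size cannot be known from the documents.

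The effect is on descriptive estimates, not on a test. It is worth correcting because the data are few and the correction is cheap.

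**What to change.** 1. Define activity in SAP 8.3.2.
2. Keep the current 12-week summaries, labelled as adherence while using the bottle. Beside them, add a version with every FAS subject whose potential follow-up includes Day 84, that is, first dose at least 83 days before study termination (Day 1 + 83 days = Day 84). Use 2 × (84 − physician-directed interruption days). State that days without openings count as missed, since SAP 8.1 bars imputation unless specified, and that time after a stop recorded as non-compliance stays counted. As far as documented, remove from numerator and denominator bottle malfunction, dosing from a non-activated bottle, and time after physician-directed discontinuation, consent withdrawal or start of commercial LUM/IVA. Present the two versions as a sensitivity range, not a strict bound.
3. For the all-duration endpoint, add a version ending at the CRF last-dose date, and report by arm how many subjects have a CRF date later than the last activity.
4. Restore the by-arm row, with reasons, for stopped use of the technology. Report 12-week exclusions by arm and reason, separating administrative truncation from stopping.
5. Reconcile SAP 8.3 with SAP 8.1 and 8.3.2.

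The cost is SAP wording, a population flag, an end-date variable, a disposition row and an exclusion table. SAP 8.3.2 already uses openings, dose dates and reported interruptions. The eCRF is not provided, so it cannot be seen whether malfunction, consent-withdrawal or commercial-start dates were collected. The downside to state openly is that undocumented non-capture would be scored as missed.

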8.4 Safety Analysis

The overall safety profile of study drug will be assessed in terms of the following safety and tolerability endpoints:

- Treatment-emergent adverse events (TEAEs)
- Clinical laboratory values (i.e., liver function tests)
- Vital signs
- Ophthalmological examinations

Safety endpoints will be analyzed based on the Safety Set. Only a descriptive analysis of safety will be performed.

8.4.1 Adverse Events

AEs will be classified as pretreatment AEs, TEAEs, or post-treatment AEs, defined as follows:

Pretreatment AE: any AE that started before the first dose date of study drug

TEAE: any AE that worsened (either in severity or seriousness) or that was newly developed at or after the first dose date of study drug through the end of the TE period

Post-treatment AE: any AE that worsened (either in severity or seriousness) or that was newly developed beyond the TE period

For AEs with completely missing or partially missing start dates, if there is no clear evidence that the AEs started before or after study treatment, the AEs will be classified as TEAEs.

Details for imputing missing or partial start dates of adverse events are described in [Appendix D](#).

AE overall summary table, TEAEs by SOC and PTs summary table, TEAEs by PTs summary table, related TEAEs by SOC and PTs summary table will be presented by study arms and overall. In addition, SAEs, AEs, TEAEs leading to treatment discontinuation, TEAEs leading to drug interruption will be listed.

8.4.2 Clinical Laboratory

For the on-treatment laboratory measurements, the raw values and change from baseline values of the liver function test results will be summarized in SI units by study arms at each visit.

The abnormal (high) LFT test results will be listed.

The abnormal (high or low) chemistry and hematology test results will be listed.

The abnormal urine or serum pregnancy test for female subjects of childbearing potential will be listed.

8.4.3 Vital Signs

The vital sign results will be listed.

8.4.4 Ophthalmological Examinations

Listings for subjects with abnormal ophthalmological examinations for subjects <18 years old at screening will be provided.

Listings for ophthalmological history data for all subjects will be provided.

8.4.5 Physical Examination

Listings for abnormal physical examination results will be provided.

9 INTERIM ANALYSES

Not applicable.

11 LIST OF APPENDICES

Appendix A: Schedule of Assessments

Schedules of Assessments are shown in [Table 11-1](#) and Table 11-2. These tables provide the schedule of assessments during the study from the Screening Period through the Safety Follow-up Visits.

All visits are to be scheduled relative to the Day 1 Visit.

Table 11-1 Screening Period Assessments – Study VX15-809-114

Assessment	Screening Period Day -28 to Day -1
Informed consent and assent (where applicable)	X
Inclusion and exclusion criteria review	X
Demographics	X
Height, weight, and BMI	X
Review of medical history (includes CFTR genotype) ^a	X
Ophthalmologic examination ^b	X
Prior and concomitant medications	X
Vital signs ^c	X
Physical examination ^d	X
Spirometry ^e	X
Serum pregnancy test (all female subjects of childbearing potential) ^f	X
Serum FSH ^g	X
Hematology ^h	X
Liver Function Testing ⁱ	X
AEs and SAEs	Continuous from signing of ICF or assent (where applicable) through Safety Follow-up Visit

^a Genotype testing will be performed if this is not documented in medical history. CF genotyping can be waived with documented CFTR genotype (Protocol Section **Error! Reference source not found.**).

^b An ophthalmologic examination will be conducted by either a licensed ophthalmologist or an optometrist for all subjects <18 years of age. The exam may be waived if there is documentation of an exam within 3 months of the date of informed consent (or assent, when applicable). Subjects with documentation of bilateral lens removal do not need the ophthalmologic examination (Protocol Section 11.5.6.).

^c Vital signs will be assessed following a 5-minute rest in the seated or supine position.

^d Physical examination of all body systems (Protocol Section **Error! Reference source not found.**).

^e Spirometry may be performed pre- or postbronchodilator (Protocol Section 11.5.5)

^f Any female subject initiating LUM/IVA combination therapy who is considered to be of childbearing potential should have a serum pregnancy test. Women of childbearing potential are defined as: female subjects after puberty unless they are postmenopausal for at least 1 year and have documented FSH levels within the postmenopausal reference range of the performing laboratory, or are surgically sterile.

^g Serum FSH levels will be measured for any suspected postmenopausal female subjects with at least 12 months of continuous spontaneous amenorrhea.

^h Blood samples will be collected for clinical laboratory assessments (Protocol Section 11.5.2).

ⁱ Liver function testing (alanine aminotransferase [ALT], aspartate aminotransferase [AST], gamma-glutamyl transpeptidase [GGT], alkaline phosphatase [ALP], and total bilirubin) must be performed at the scheduled visits (Protocol Section 11.5.2).

Table 11-2 Treatment Period and Safety Follow-up Visit Assessments – Study VX15-809-114

Event/Assessment	Day 1	Week 12	Week 24	Week 36	Week 48	Safety Follow-up Week 52 ^a
Clinic visit	X	X	X	X	X	X
Vital signs ^b	X	X	X	X	X	X
Physical examination ^c					X	X ^d
Liver Function Testing ^e	X	X	X	X	X	X
Urine pregnancy test (all female subjects of childbearing potential)	X	X	X	X	X	X
Randomization ^f	X					
Standardized education on adherence	X					
Concomitant medications, treatments, and procedures	X	X	X	X	X	X
Smart Adherence Technology-Reported Adherence ^g		X	X	X	X	

LUM/IVA drug count ⁱ		X	X	X	X	
Ophthalmologic examination ^j					X	
AEs and SAEs	Continuous from signing of ICF or assent (where applicable)					
LUM/IVA resupply	Every 3 months throughout study					

^a The Safety Follow-up Visit is 28 (\pm 7) days after the last dose of LUM/IVA (Protocol Section 8.1.3).

^b Vital signs will be assessed following a 5-minute rest in the seated or supine position.

^c Symptom-targeted PEs will occur at any time during the study if triggered by AEs or if deemed necessary by the investigator.

^d Required for subjects who do not begin commercial LUM/IVA after Week 48 only.

^e Day 1 only blood draws will be collected before the first dose of LUM/IVA. Liver function testing (alanine aminotransferase [ALT], aspartate aminotransferase [AST], gamma-glutamyl transpeptidase [GGT], alkaline phosphatase [ALP], and total bilirubin) must be performed at the scheduled visits (Protocol Section 11.5.2).

^f Randomization must occur after all inclusion and exclusion criteria are met and before the first dose of LUM/IVA. Randomization will be done through IWRS.

^g Data will be collected for all subjects throughout the study in real-time. Subjects in Study Arm A will review data with physicians at study visits.

ⁱ LUM/IVA drug count will be collected at the end of specified study visits.

^j See Protocol Section 11.5.6.

Appendix B: Analysis Visit Windows for Safety and Adherence/PROs Assessments

Table 11-3 Analysis Visit Windows for Study Assessments

Assessment	Analysis Visit ^a	Target Study Day ^b	Analysis Visit Window (in study days)
Safety Assessment			
LFTs;	Baseline	Day 1	≤1
Vital Signs;	Week 12	Day 85	[2, 127]
	Week 24	Day 169	[128, 211]
	Week 36	Day 253	[212, 295]
	Week 48	Day 337	[296, 379]
	Safety Follow-up (Week 52)	Day 364	Use nominal visit
Adherence			
	Baseline	Day 1	≤1
Subject Satisfaction with Smart Adherence Technology	Week 12	Day 85	[2, 127]
	Week 24	Day 169	[128, 211]
	Week 36	Day 253	[212, 295]
	Week 48	Day 337	[296, 379]

Notes:

The analysis visit windows will be applied using the following rules for both scheduled and unscheduled visits:

1. If no numerical measurement is available within a visit window, the measurement will be considered missing for the visit.
2. If there is more than 1 numerical measurement available within the same visit window, use the following rules:
 - a. For Adherence: if there are multiple measurements within a visit window, the measurement at the scheduled visit will be used. Otherwise,
 - i. If there are no measurements at the scheduled visit, then the measurement closest to the target day will be used; or
 - ii. If there are multiple measurements with the same distance to the target day, the latest measurement will be used.
 - b. For safety parameters: if there are multiple measurements within a visit window,
 - i. The measurement closest to the target day will be used; or
 - ii. If there are multiple measurements within the same distance from the target day, the latest measurement will be used.

^a Analysis Visit is used to report data in tables and figures, but not listings.

b Analysis Visit is used to report data in tables a
Target day time point per protocol is predose.

